15.3. Analysis of Urine PK Data

A listing of individual PK urine sample collection start and stop dates/times as well as urine volumes will be provided for each urine collection. Amounts of urine excreted over each planned collection interval for each treatment will be summarized using descriptive statistics for the PK Analysis Set.

The following parameters will be calculated from the urine data:

$A_{e(t1-t2)}$	By-interval amount excreted in urine during the pooled collection interval from t1 to t2 over the following intervals: 0-2 hr, 2-4 hr, 4-6 hr, 6-12 hr, 12-24 hr, 24-36 hr and 36-48 hr
$A_{e(0-\text{last})}$	Cumulative amount excreted in urine during the pooled collection intervals
$f_{e(t1-t2)}$	By-interval fraction of dose (reported as percent) excreted in urine during the pooled collection interval from t1 to t2
$f_{e(0-\text{last})}$	Cumulative fraction of dose (reported as percent) excreted in urine during the pooled collection intervals
CL_r	Renal clearance (L/h), calculated as $A_{e(0-\text{last}2)}$ divided by $AUC_{(0-\text{last})}$.

Urine PK parameters will be summarized by treatment using descriptive statistics for the PK Analysis Set. A participant listing of individual urine PK parameters for each treatment will be provided. Geometric mean and individual cumulative percent CS-1103 excreted in urine versus time curves by dose will also be presented on linear scale.

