8.4 Pharmacokinetics

8.4.1 Collection of Samples

Blood samples of approximately 2 mL and pooled urine will be collected for measurement of plasma and urine concentrations of CS-1103; respectively, at times as specified in SoA ([Section 1.3](#)) and [Table 2](#) during treatment. The timing of sampling may be altered during the course of the study based on newly available data (e.g., to obtain data closer to the time of peak plasma concentrations) to optimize the PK sample collection schedule for PK parameter calculations. Up to 2 additional blood collections may be added, pooled urine collections may be extended, and discharge may be delayed for up to 8 hours to optimize PK assessment without preparation of an amendment. The timing of PK (both plasma and urine) may be adjusted based on emerging data. In case that CS-1103 half-life is less than 4 hours, PK sampling may be discontinued at a time earlier than 48 hours.

Blood samples will be taken either by direct venipuncture or an indwelling cannula inserted in a forearm vein. On the day of CS-1103 administration, samples should be collected in the contralateral (opposite) arm from the one being used for drug infusion. The actual date and time (24-hour clock time) of each sample will be recorded. Samples will be used to evaluate the PK of CS-1103-01. Each plasma sample will be divided into 2 aliquots (1 each [primary and a back-up]). Samples collected for analyses of CS-1103 plasma concentration may also be used to evaluate safety or efficacy aspects related to concerns arising during or after the study.

The window for the blood collections is detailed in [Table 2](#).

Urine samples for the determination of CS-1103-01 will be collected over the pooled intervals as specified in [Table 2, Section 1.3](#). The actual start and stop date/time of each pooled urine collection as well as the volume of each pooled collection will be recorded. The site will also document whether the entire voided urine was collected for each interval (and complete void volume was recorded).

Blood and pooled urine samples will be collected, labeled, stored, and shipped as detailed in the Laboratory Manual.

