$A_{e(t1-t2)}$	By-interval amount excreted in urine during the pooled collection interval from t_1 to t_2
$A_{e(0-last)}$	Cumulative amount excreted in urine during the pooled collection intervals
$f_{e(t1-t2)}$	By-interval fraction of dose (reported as percent) excreted in urine during the pooled collection interval from t_1 to t_2
$f_{e(0-last)}$	Cumulative fraction of dose (reported as percent) excreted in urine during the pooled collection intervals
CL_r	Renal clearance calculated as $A_{e(0-last)}/AUC_{(0-last)}$

Note: No dose correction for the sodium salt will be required for dose-dependent parameters, as both CS-1103 dose and plasma concentrations will be based on the weight of the tetrasodium salt.

Additional urine parameters may be calculated if deemed appropriate. Further details will be provided in the SAP.

Any changes in the timing or addition of time points for any planned study assessments must be documented and approved by the relevant study team member and then archived in the Sponsor and study site study files but will not constitute a protocol amendment. The IRB will be informed of any safety issues that require alteration of the safety monitoring scheme or amendment of the ICF.

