10.1.7 Committees Structure

10.1.7.1 Safety Review Committee

A SRC has been appointed for this study. The SRC is a group of clinicians and/or scientists who are appointed to monitor the safety and scientific integrity of a human research intervention, and to make recommendations regarding for escalation to the next planned dose level, escalation to an intermediate dose (a dose lower than the next planned dose), repeating a dose level, suspension of the dose escalation until further review of study data can be made, as to whether the stopping rules have been met, or stop dose escalation and termination of the study, etc. The composition of the committee is dependent upon the scientific skills and knowledge required for monitoring the particular study.

The SRC will consist, at a minimum, of the Principal or Sub-Investigator, Medical Monitor, and Sponsor's qualified designee. The SRC is responsible for reviewing and evaluating blinded safety and PK data for the most recently dosed cohort, cumulatively obtained data, and subsequently at regularly scheduled meetings and for the dose selection during dose escalation. The committee may also meet in ad hoc meetings at its discretion as needed in response to events occurring in the study.

Participant safety will be continuously monitored by the SRC, which includes safety signal detection at any time during the study.

In addition, an early aggregated safety data review will be performed, the goal of which is to allow for a cautious, stepwise approach to study treatment administration/dose escalation. An initial sentinel safety review by an Investigator for this study is planned for the first 2 participants who are dosed in each of the 5 cohorts and have provided safety and tolerability data for 24 hours after administration of a single dose prior to dosing the remaining participants within each cohort (see [Section 4.1](#)).

All safety results for at least 48 hours and preliminary PK data through at least Day 2 (24 hours postdose) for at least 6 out of the 8 participants within a cohort will be summarized

and reviewed by the SRC for agreement of next steps in dose escalation, due to the short half-life of the compound.

In particular, data will be reviewed by the Sponsor for identification of events that would potentially contribute to a requirement to pause/stop dose escalation or the study. See [Section 4.6](#) for stopping criteria details.

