15.2. Pharmacokinetic Parameters

For PK parameter calculations, predose samples that are BLQ or missing will be assigned a numerical value of zero. Any anomalous concentration values observed at predose will be identified in the study report and used for the computation of PK parameters. Pharmacokinetic parameters will be computed if the anomalous concentration is not greater than 5% of the observed maximum concentration (C_{max}). If the anomalous concentration is greater than 5%

of C_{max} , the PK parameters for the given subject will be calculated and reported in the listing, but excluded from statistical summaries and analyses.

Any other BLQ concentrations will be assigned a value of zero if they precede quantifiable samples in the initial portion of the profile. A BLQ value that occurs between quantifiable data points, especially prior to C_{max} , will be evaluated to determine if an assigned concentration of zero makes sense, or if exclusion of the data is warranted. Following C_{max} , BLQ values embedded between 2 quantifiable data points will be treated as missing when calculating PK parameters. If a BLQ value occurs at the end of the collection interval (after the last quantifiable concentration), it will be set to zero. If consecutive BLQ concentrations are followed by quantifiable concentrations in the terminal portion of the concentration curve, these quantified values will be excluded from the PK analysis by setting them to missing, unless otherwise warranted by the concentration-time profile.

The following plasma PK parameters will be estimated for CS-1103 by non-compartmental methods using actual elapsed time from the end of infusion. A minimum of 3 quantifiable postdose concentrations will be required for calculation of PK parameters.

C_{max} Maximum concentration, obtained directly from the observed concentration versus time data

C_{EOI} Concentration at the end of the 10-minute IV infusion

t_{max} Time to C_{max}

[figure not shown]
$AUC_{(0-inf)}$ Area under the plasma concentration-time curve from time zero (end of the 10-minute IV infusion) extrapolated to infinity, calculated by linear up/log down trapezoidal summation

$AUC_{(0-last)}$ Area under the plasma concentration-time curve from time zero to the time of the last quantifiable concentration, calculated by linear up/log down trapezoidal summation

CL Systemic clearance, calculated as dose divided by $AUC_{(0-inf)}$

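### Renal clearance divides urine recovery over all collection intervals by a plasma AUC that may end earlier, so CLr can be biased high

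*SAP*

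**What the plan says.** Protocol 8.4.3 (urine parameter table) has "Renal clearance calculated as" Ae(0-last)/AUC(0-last), where Ae(0-last) is the "Cumulative amount excreted in urine during the pooled collection intervals". SAP 15.3 has "Renal clearance (L/h), calculated as" Ae(0-last2) divided by AUC(0-last). The subscript 'last2' is explained neither there nor in the SAP abbreviation list. The SAP takes by-interval amounts "over the following intervals: 0-2 hr, 2-4 hr, 4-6 hr, 6-12 hr, 12-24 hr, 24-36 hr and 36-48 hr".

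The denominator, in SAP 15.2, is the "Area under the plasma concentration-time curve from time zero to the time of the last quantifiable concentration". For later samples the SAP says: "If a BLQ value occurs at the end of the collection interval (after the last quantifiable concentration), it will be set to zero". They therefore add nothing to AUC(0-last).

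Two SAP 15.2 rules remove poorly determined parameters from the summaries: more than 30% extrapolated AUC, and an adjusted R-squared below 0.800. Neither lists CLr.

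The time origin also differs. SAP 15.2 counts plasma time from the end of infusion. Protocol 8.4.3 counts it from the start for the final parameters.

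**The concern.** The two 'last' times share a name but not a definition. The numerator ends when urine collection ends, and the denominator ends when the assay can no longer quantify the drug in plasma. Any drug excreted in between is counted on top of the ratio without its matching plasma exposure below.

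The protocol expects this situation. Section 4.2 plans around a short half-life, and section 10.1.7.1 justifies the committee's data window "due to the short half-life of the compound".

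CLr is a named secondary endpoint. Two misleading results are possible:

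- If nearly all the dose is recovered in urine, reported CLr can exceed total CL, because CL uses AUC(0-inf) and CLr uses the shorter AUC(0-last).
- If low doses become unquantifiable sooner, CLr can appear to fall as dose rises although true CLr is constant. That pattern resembles saturable renal excretion.

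**Working it through.** Neither document states a CLr value, LLOQ or half-life, so there is no figure to reproduce.

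**Inputs from the documents.** At 40 mg/kg, projected C0 is 340 µg/mL and AUC(0-last) is 318 µg·h/mL (Protocol 4.5, footnote). Doses run from 2.7 to 40 mg/kg (Protocol 4.1). Infusion lasts 10 minutes. Plasma times are those of the detailed schedule in Protocol 1.3. Urine is planned to 48 h.

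**Assumptions.** PK is dose-linear, CLr is constant and urine collection is complete. The projected AUC is treated as total AUC, and the 3000 mg cap is ignored. LLOQ is 0.01, 0.1 or 1 µg/mL. Samples from 4 h on are timed from infusion start.

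**Direction.** Ae(0-48) = CLr × AUC(0-48), so reported CLr = CLr × AUC(0-48)/AUC(0-tlast). The relative bias is AUC(0-48)/AUC(0-tlast) − 1, which is never negative. If x is the extrapolated fraction of AUC, the bias is at most x/(1 − x): 5.3%, 11.1%, 25% and 42.9% for x of 5%, 10%, 20% and 30%.

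**One compartment.** k = 340/318 = 1.069 per h, so the half-life is 0.693/1.069 = 0.65 h. At the end of infusion the concentration is (1 − e^(−k/6))/(k/6) = 0.916 of C0. The AUC fraction beyond a sample taken τ hours after the end of infusion is f = 0.916·e^(−kτ), and the bias is f/(1 − f).

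- 2.7 mg/kg, LLOQ 1: C0 = 340 × 2.7/40 = 22.95, so the end-of-infusion value is 21.0 µg/mL. It reaches 1 µg/mL after ln(21.0)/1.069 = 2.85 h, so the last quantifiable sample is at τ = 2.5 h. Then f = 0.916 × e^(−2.673) = 0.0632 and the bias is 0.0632/0.9368 = 6.8%.
- 40 mg/kg, LLOQ 1: the end-of-infusion value is 311 µg/mL and reaches 1 µg/mL after 5.37 h, so the last quantifiable sample is the 4 h one (τ = 3.83 h). Then f = 0.0152 and the bias is 1.5%.

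| Assumed LLOQ (µg/mL) | Last quantifiable, 2.7 mg/kg | Bias | Last quantifiable, 40 mg/kg | Bias |
|---|---|---|---|---|
| 0.01 | 6 h | +0.2% | 8 h | +0.02% |
| 0.1 | 4 h | +1.5% | 6 h | +0.2% |
| 1 | 2.7 h | +6.8% | 4 h | +1.5% |

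**Two compartments, same C0 and AUC.** The assumed slow phase has a half-life of 2, 4 or 8 h and carries 5%, 20% or 30% of AUC. Over all these cases the bias is +0.3% to +39% at 2.7 mg/kg and 0% to +7% at 40 mg/kg. Selected cases, cohorts 1 to 5:

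| Slow phase | LLOQ (µg/mL) | Bias by cohort |
|---|---|---|
| 4 h, 20% of AUC | 1 | 18.5, 11.9, 5.3, 5.3, 2.6% |
| 8 h, 20% | 1 | 22.6, 16.9, 10.9, 7.3, 7.3% |
| 8 h, 30% | 1 | 38.6, 26.9, 11.4, 11.4, 3.4% |
| 8 h, 30% | 0.1 | 11.4, 3.4, 0.9, 0.9, 0% |
| 8 h, 30% | 0.01 | 0.9, 0, 0, 0, 0% |

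The 39% and 7% extremes come from different cases. In the 39% case the slow-phase intercept at 40 mg/kg is 0.30 × 318 × 0.693/8 = 8.27 µg/mL, which scales to 0.56 µg/mL at 2.7 mg/kg. The whole slow phase then lies below a 1 µg/mL LLOQ. AUC(0-48) is 21.36 µg·h/mL, of which 15.41 is accrued by the last quantifiable sample (2.17 h), and 21.36/15.41 = 1.386.

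In every case the lowest dose had the largest bias or tied for it.

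**Time origin.** In the one-compartment case the infusion period holds 1 − 0.916 = 8.4% of AUC. Leaving it out multiplies CLr by 1/0.916, about 9% high at every dose.

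**The case against.** The strongest reply is that the effect is small and visible. On the protocol's own projection as a single exponential it reaches 6.8% only with an LLOQ of 1 µg/mL, which is 1/22.95 = 4.4% of the projected cohort 1 C0. At an LLOQ of 0.01 µg/mL it stays under 1% even with the slowest phase tried. CLr is a descriptive summary of six active participants per cohort. No hypothesis is tested, dose proportionality is not analysed for secondary PK parameters (SAP 15.2), and the safety committee sees plasma PK (SAP 4.1). The extrapolated percentage and by-interval urine amounts are reported, so a careful reader could spot the mismatch and recompute. 'last2' may be a slip or may mean a truncated urine amount. Incomplete urine collection pushes CLr the other way.

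All of this limits the consequence. None of it aligns the windows or tells the analyst which numerator to use.

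A reader might also infer three stronger points that the documents do not support:

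- **That the plan has plasma sampling stop while urine collection continues.** Protocol 8.4.1 says "PK sampling may be discontinued at a time earlier than 48 hours" if the half-life is under 4 h, but this follows a sentence about adjusting plasma and urine timing together and may cover both. The allowance to extend urine collection stands beside one for extra blood samples.
- **That the product's mechanism is at stake.** Protocol 2.2 describes faster renal clearance of methamphetamine. The endpoint is CLr of CS-1103, in volunteers who must screen negative for drugs of abuse.
- **That the bias is certain or unlimited.** It is bounded by x/(1 − x). What is missing is an exclusion rule that covers CLr.

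**Conclusion.** The mismatch is real in both documents, and any bias that it causes is upward. It arises only when plasma becomes unquantifiable before urine collection ends. The dose pattern rests on dose-linear PK and a fixed LLOQ.

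The size cannot be settled from the documents. On the projected exposure alone it is a few percent or less at most settings. It passes 10% at the lowest dose only if a slower phase carries an appreciable share of AUC and the LLOQ is high relative to that phase. A reader should not conclude that cohort 1 will be substantially wrong, because that depends on assay and disposition values not given here. In most cases examined the time-origin conflict could matter more, if the infusion area is left out.

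This is an inexpensive correction to a secondary-endpoint formula, best made before unblinding. It does not threaten the trial's primary safety objective.

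**What to change.** In SAP 15.3 and the urine parameter table of Protocol 8.4.3, replace the formula, including 'last2', with CLr = Ae(0-t)/AUC(0-t) over one common interval. Choose one rule in advance:

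1. t is the end of the last urine interval that is not later than the participant's last quantifiable plasma time; or
2. t is the end of the urine window, with AUC carried there using λz where λz meets the SAP's fit rule.

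In the same edit, reconcile the AUC time origin so that plasma and urine start together and the infusion area is included.

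Matching the windows removes this bias by construction, provided the carried-forward area in option 2 is accurate. All data needed are already planned. Option 1 may leave only the earliest urine intervals in low-dose participants: with a last quantifiable time of 2.7 h, only 0-2 h remains. Option 2 keeps all the urine data but leaves some bias if the slow phase lies below the LLOQ, because λz is then estimated from the faster phase.

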16. SAFETY OUTCOMES

All outputs for safety outcomes will be based on the Safety Analysis Set.

There will be no statistical comparisons between the treatment groups for safety data, unless otherwise specified within the relevant section.

16.1. Adverse Events

Adverse Events (AEs) will be coded Medical Dictionary for Regulatory Activities (MedDRA) central coding dictionary, the latest version.

Treatment emergent adverse events (TEAEs) are defined as AEs that started or worsened in severity on or after the date/time of study treatment administration.

Pretreatment AEs are defined as AEs occurring and ending prior to dosing or occurring prior to dosing and continuing into the treatment period without worsening. These events will be presented in the listings only and are not included in the tabular summary of AEs. See Appendix 2 for handling of partial dates for AEs. In the case where it is not possible to define an AE as treatment emergent or not, the AE will be classified by the worst case, i.e. treatment emergent.

16.1.1. All TEAEs

Incidence of TEAEs will be presented by System Organ Class (SOC) and Preferred Term (PT) and broken down further by maximum severity and relationship to study medication.

16.1.1.1. SEVERITY

Severity is classed as mild/ moderate/ severe (increasing severity). TEAEs starting after the study treatment administration with a missing severity will be classified as severe. If a participant reports a TEAE more than once within that SOC/ PT, the AE with the worst-case severity will be used in the corresponding severity summaries.

16.1.1.2. RELATIONSHIP TO STUDY MEDICATION

Relationship, as indicated by the Investigator, is classed as “reasonable possibility” or “not a reasonable possibility”. A “related” TEAE is defined as a TEAE with a relationship to study treatment as “reasonable possibility” to study treatment. TEAEs with a missing relationship to study treatment will be regarded as “reasonable possibility” to

study treatment. If a participant reports the same AE more than once within that SOC/ PT, the AE with the worst-case relationship to study medication will be used in the corresponding relationship summaries.

All AE tabulations will be performed by treatment, including all placebo and active-treated subjects combined when applicable. Incidence of TEAEs will be tabulated by the following:

- An overall summary across all SOC and PT, any TEAE, any related TEAE, severe, serious, leading to study discontinuation, leading to death, and TEAEs by maximum severity
- By SOC and PT
- By SOC and PT for related TEAEs
- By SOC, PT and Maximum Severity
- By SOC, PT and Maximum Severity for related TEAEs

16.1.2. TEAEs Leading to Discontinuation from Study

Treatment emergent adverse events leading to discontinuation from study will be identified by using the response to the question “Did the AE cause the subject to discontinue from the study?” on the AE page of the electronic Case Report Form (eCRF) and listed

16.1.3. Serious Adverse Events

Serious adverse events (SAEs) are those events recorded as “Serious” on the Adverse Events page of the (e)CRF and will be listed.

16.2. Deaths

If any participants die during the study as recorded on the “deaths” page of the (e)CRF, the information will be presented in a data listing.

16.3. Laboratory Evaluations

Laboratory results, with units provided by the local laboratory, will be included in the reporting of this study for hematology, clinical chemistry, coagulation, and urinalysis. A list of laboratory assessments to be included in the outputs is included in Table 5 of the protocol.

Protocol-specified clinical laboratory tests will be listed and summarized using descriptive statistics. Clinical laboratory data collected during study conduct, which were not required per protocol, such as for special testing to evaluate an AE, will be listed separately and not summarized.

Quantitative laboratory measurements reported as ‘< X’, i.e., below the lower limit of quantification, or ‘> X’, i.e., above the upper limit of quantification, will be converted to X for the purpose of quantitative summaries, but will be presented as recorded, i.e., as ‘< X’ or ‘> X’ in the listings.

The following summaries will be provided for laboratory data:

- Actual and change from baseline by visit and treatment (for quantitative measurements)
- Shift from baseline according to normal range criteria at each post-baseline visit
- Listing of laboratory results outside the normal range

16.3.1. Laboratory Reference Ranges

Quantitative laboratory measurements will be compared with the relevant laboratory reference ranges by the laboratory vendor and categorized as:

- Low: Below the lower limit of the laboratory reference range.
- Normal: Within the laboratory reference range (upper and lower limit included).
- High: Above the upper limit of the laboratory reference range.

[figure not shown]
Clinical laboratory reference/normal ranges will be listed.

16.4. ECG Evaluations

The following ECG data will be reported for this study: PR, QRS, QT, QTcF, and HR. Replicate measurements will be averaged for use in summary tables.

Assessment of ECG (Investigator’s judgment) for each parameter will be recorded as following:

- Normal
- Abnormal, Not Clinically Significant (NCS)
- Abnormal, Clinically Significant (CS)

The following summaries will be provided for ECG data:

- Actual and change from baseline by visit, timepoint and treatment
- Number (%) of subjects with clinically noteworthy values postdose
- Listing of subjects with clinically noteworthy values

